15.2 Appendix B: Instructions for the Subject.....	45
15.3 Appendix C: Face Diagram	48
16. REFERENCES.....	49

STUDY SYNOPSIS

Title:	A Multi-Center, Double-Blind, Randomized, Vehicle-Controlled, Parallel-Group Study to Compare Perrigo UK FINCO Clindamycin Phosphate and Benzoyl Peroxide Topical Gel 1.2%/3.75% to Valeant Pharmaceuticals North America, LLC Onexton™ Topical Gel (Clindamycin Phosphate and Benzoyl Peroxide Gel 1.2%/3.75%), and Both Active Treatments to a Vehicle Control in the Treatment of Acne Vulgaris
Study Period:	12 weeks (84 Days)
Study Medication:	
 1. Clindamycin Phosphate and Benzoyl Peroxide Topical Gel 1.2%/3.75%, [REDACTED]. 2. Onexton™ Topical Gel (Clindamycin Phosphate and Benzoyl Peroxide Gel 1.2%/3.75%), Valeant Pharmaceuticals North America, LLC 3. Vehicle of test product, [REDACTED]
Study Objectives:	To compare the safety and efficacy profiles of Perrigo UK FINCO Clindamycin Phosphate and Benzoyl Peroxide Topical Gel 1.2%/3.75% to Valeant Pharmaceuticals Onexton™ Topical Gel (Clindamycin Phosphate and Benzoyl Peroxide Gel 1.2%/3.75%) and to demonstrate the superior efficacy of the two active formulations over that of the vehicle in the treatment of Acne Vulgaris.
Study Design:	Subjects in this multi-center, double-blind, randomized, vehicle-controlled, parallel-group study will be admitted into the study only after written informed consent/assent (as applicable) has been obtained and after all inclusion/exclusion criteria have been met. Male and female subjects 12 years to 40 years of age, inclusive, with acne vulgaris IGA score [REDACTED] will be eligible for enrollment.
Study Population:	Approximately [REDACTED] healthy males and females, 12 to 40 years of age, inclusive, who meet the inclusion/exclusion criteria, will be enrolled to obtain approximately [REDACTED] modified-Intent-To-Treat (mITT) and [REDACTED] per-protocol (PP) subjects.
Dosing:	Subjects will be randomized [REDACTED] to either the test product, reference product or vehicle treatment group, respectively, and will apply [REDACTED] the study medication onto six areas of the face (chin, left cheek, right cheek, nose, left forehead and right forehead) as a thin layer and avoiding contact with the eyes, lips, mouth, broken areas of the skin and mucous membranes at approximately the same time once daily for 12 weeks.
Study Visits:	
Clinical Evaluations will be performed at:
 
 1. Visit 1/Day 1 (Baseline) 2. Visit 2/Week 4/Day 28 (± 4 days)(Interim) 3. Visit 3/Week 8/Day 56 (± 4 days)(Interim) 4. Visit 4/Week 12/Day 84 (± 4 days)(End of treatment/End study) 
Safety will be assessed by monitoring adverse events at each visit and at the

Protocol No: PRG-NY-15-003

	Week 2/Day 15 (± 4 days) Telephone Contact.
Evaluations:	The number of facial inflammatory and non-inflammatory lesions as well as the Investigator's Global Assessment (IGA) will be recorded at baseline and all subsequent visits.
Endpoints:	
The two primary efficacy endpoints will be the:
 
1) Mean percent change from baseline to Week 12 (Day 84) in the inflammatory (papules and pustules) lesion count and2) Mean percent change from baseline to Week 12 (Day 84) in the non-inflammatory (open and closed comedones) lesion count. 
The secondary endpoint will be the proportion of subjects at Week 12 with a clinical response of "success", defined as an IGA score that is at least 2 grades less than the baseline assessment.

Safety:	The incidence of all adverse events reported during the study will be summarized by treatment group. Equivalence of the test and reference with regard to safety will be evaluated by comparing the nature, severity and frequency of their adverse event profiles. In addition, the test and reference treatments' frequency and distribution of application site reactions of erythema, dryness, scaling/peeling, burning/stinging, erosion, edema, pain and itching will be summarized and compared descriptively.

ABBREVIATIONS

AE	Adverse Event
ANOVA	Analysis of Variance
CMH	Cochran–Mantel–Haenszel test
CRF	Case Report Form
DCF	Data Correction Form
FDA	US Food and Drug Administration
GCP	Good Clinical Practices
ICH	International Conference on Harmonization
IGA	Investigator's Global Assessment
IRB	Institutional Review Board
ITT	Intent- to-treat (population)
IU	International Unit
IUD	Intra-Uterine Device
LOCF	Last Observation Carried Forward
MedDRA	Medical Dictionary for Regulatory Activities
miITT	Modified Intent-to-Treat (population)
NSAID	Non-Steroidal Anti-Inflammatory Drug
OTC	Over the counter
PI	Principal Investigator
PP	Per- protocol (population)
Rx	Prescription
SAE	Serious Adverse Event
SAP	Statistical Analysis Plan
SPF	Sun Protection Factor
Sub-I	Sub-Investigator
UPT	Urine Pregnancy Test

1. BACKGROUND

Onexton™ Topical Gel (Clindamycin Phosphate and Benzoyl Peroxide Gel 1.2%/3.75%), is indicated for the topical treatment of Acne Vulgaris. Perrigo UK FINCO has developed a generic formulation of Clindamycin Phosphate and Benzoyl Peroxide Topical Gel 1.2%/3.75%.

2. STUDY OBJECTIVES

The objectives of this study are to compare the efficacy and safety profiles of Perrigo UK FINCO, Clindamycin Phosphate and Benzoyl Peroxide Topical Gel 1.2%/3.75%, and Onexton™ Topical Gel (Clindamycin Phosphate and Benzoyl Peroxide Gel 1.2%/3.75%), and to show the superior efficacy of the two active formulations over that of the vehicle in the treatment of Acne Vulgaris.

2.1 Endpoints

The two primary efficacy endpoints will be the:

- 1) Mean percent change from baseline to Week 12 in the inflammatory (papules and pustules) lesion count and
- 2) Mean percent change from baseline to Week 12 in the non-inflammatory (open and closed comedones) lesion count.

The secondary endpoint will be the proportion of subjects at Week 12 with a clinical response of "success", defined as an IGA score that is at least 2 grades less than the baseline assessment.

2.2 Safety

Safety of the test and reference products will be compared by evaluating the nature, severity and frequency of their adverse event profiles. All adverse events that occur during the study will be recorded. Descriptions of reactions or complaints will include the approximate date of onset, the date the adverse event ended, the severity of the adverse event, and the outcome. Comparisons between the treatment groups will be made by tabulating the frequency of Subjects with one or more adverse events (classified into MedDRA terms) during the study. Pearson's Chi-Square test or Fisher's Exact test, whichever is most appropriate, will be used to compare the proportion of subjects in each treatment group with any adverse event. The adverse events reported by at least five percent of the subjects in any treatment group will be summarized descriptively.

3. STUDY DESIGN

3.1 Type/Design of Study

Protocol No: PRG-NY-15-003

Subjects in this multi-center, double-blind, randomized, vehicle-controlled, parallel-group study will be assigned [REDACTED] to test product, reference product, or vehicle, respectively. [REDACTED]

[REDACTED] the assigned study medication will be applied topically [REDACTED] onto six areas of the face (chin, left cheek, right cheek, nose, left forehead and right forehead), avoiding contact with the eyes, lips, mouth, broken skin areas and mucous membranes once daily around the same time for 12 weeks.

Subjects will be males and females, ≥ 12 to ≤ 40 years of age, with [REDACTED] facial acne vulgaris with an inflammatory lesion (papules and pustules) [REDACTED] and a non-inflammatory lesion (open and closed comedones) [REDACTED] and [REDACTED] nodulocystic lesions (i.e., nodules and cysts) on the face including those present on the nose. Visits to the study site are scheduled at baseline (Day 1) and Weeks 4, 8, and 12. A telephone contact will be made at Week 2.

3.2 Study Population

Male and female subjects, 12 to 40 years of age, inclusive, with a clinical diagnosis of at least moderate facial acne vulgaris.

4. SELECTION AND WITHDRAWAL OF STUDY SUBJECTS

4.1 Inclusion Criteria

Subjects **must** meet all of the following criteria:

1. Subject must sign an Institutional Review Board (IRB) approved written informed consent for this study. Subjects under the legal age of consent must sign an IRB approved written informed consent/assent in addition to a parent or legally authorized representative.
2. Subjects must be male or female, 12 to 40 years of age, inclusive.
3. Subjects must have a definite clinical diagnosis of facial acne vulgaris [REDACTED]
[REDACTED]
4. Subjects must have a baseline Investigator's Global Assessment (IGA) Score [REDACTED].
[REDACTED]
5. Subjects must be willing and able to understand and comply with the requirements of the study, apply the medication as instructed, refrain from use of all other topical acne medication or topical antibiotics during the 12-week treatment period, return for the required treatment period visits, comply with therapy prohibitions, and are able to complete the study.
6. Subjects must be in general good health and free from any clinically significant disease, other than acne vulgaris, that might interfere with the study evaluations.
7. [REDACTED]

4.2 Exclusion Criteria

Subjects may **not** be selected if any of the following criteria exist:

1. Subjects, who are pregnant, breastfeeding, or planning a pregnancy within the study participation period.
2. Presence of [REDACTED] nodulocystic lesions (i.e. nodules and cysts).
3. Acne conglobata, acne fulminans, or secondary acne (chloracne, drug-induced acne, etc.).
4. [REDACTED]
5. [REDACTED]
6. [REDACTED]
7. Presence of any other facial skin condition that might interfere with acne vulgaris diagnosis and/or assessment [REDACTED]
8. Excessive facial hair (e.g. beards, sideburns, moustaches, etc.) that would interfere with diagnosis or assessment of acne vulgaris.
9. [REDACTED]
10. [REDACTED]
11. [REDACTED]
12. [REDACTED]
13. [REDACTED]
14. [REDACTED]

Protocol No: PRG-NY-15-003

15. Use of medications known to exacerbate acne (Vitamin B12, lithium, corticosteroids; Vitamin B12, etc. as part of a multivitamin regimen is allowed).

16. [REDACTED]

17. [REDACTED]

18. [REDACTED]

19. [REDACTED]

20. [REDACTED]

21. [REDACTED]

22. Subject consumes excessive alcohol, abuses drugs, or has a condition that could compromise the subject's ability to comply with study requirements.

23. [REDACTED]

24. Participation in any clinical study involving an investigational product, agent or device (that might influence the intended effects or mask the side effects of study medication) in the 4 weeks (30 days) prior Visit 1/Day 1 (Baseline) or throughout the study.

25. Previous enrollment in this study or current enrollment in this study at another participating site.

26. [REDACTED]

27. Use of tanning booths, sun lamps, sunbathing or excessive exposure to the sun [REDACTED] prior to enrollment and throughout the study.

28. Subjects who in the opinion of the investigator, are unlikely to be able to follow the restrictions of the protocol and complete the study.

4.3 Prohibited Medications

The following medications/procedures are prohibited during this study:

1. Use of any treatment for acne vulgaris of the face, other than the assigned study treatment

2. Subjects should not apply the assigned drug treatment inside their nose or mouth, on their eyes, lips, or mucous membranes, or on any cuts or open wounds.
3. [REDACTED]
4. [REDACTED]
5. [REDACTED]
6. [REDACTED]
7. [REDACTED]
8. [REDACTED]
9. [REDACTED]
10. [REDACTED]
11. [REDACTED]
12. Use of tanning booths, sunbathing or other excessive exposure to sunlight should be avoided.
13. Medicines and/or products that may increase sensitivity to sunlight (apart from the IP) should be used during this study only after consultation with the Investigator.
14. [REDACTED]

4.4 Precautions

The following precautions are to be taken during this study:

Protocol No: PRG-NY-15-003

1. Subjects should avoid contact of the study medication with the eyes, mouth, lips and other mucous membranes or on any cuts or broken skin. In case of accidental exposure, the eyes should be rinsed with plenty of water.
2. [REDACTED]
3. [REDACTED]
4. [REDACTED]
5. [REDACTED]
6. [REDACTED]
7. Subjects should consult the investigator with any questions regarding concomitant medications.
8. Due to the warning contained in the label of this product, subjects should be carefully monitored for adverse events associated with severe colitis (diarrhea and bloody diarrhea). If significant diarrhea occurs, the drug should be discontinued for that subject.
9. Subjects should wash hands before and after applying study medication.
10. [REDACTED]
11. [REDACTED]
12. Subjects should avoid getting the assigned treatment on their hair or on colored fabric. Product may bleach hair or colored fabric.
13. The product should not be applied to cuts, abrasions, eczematous or sunburned skin.
14. The product should not be applied more than once daily and subjects should not use more than the recommended amount.
15. [REDACTED]
16. [REDACTED]
17. Subjects should be informed that local skin reactions (erythema, dryness, burning/stinging, erosion, edema, scaling/peeling, pain and itching) may occur.
18. Subjects should be informed that more serious side effects such as diarrhea, stomach pain and allergic reactions (e.g. severe swelling, shortness of breath, and anaphylaxis) may occur and that they should report these symptoms to the study staff immediately.
 - If a reaction suggesting sensitivity or chemical irritation occurs, the Investigator should assess the subject's condition as soon as possible (i.e., by scheduling an Unscheduled Visit, if required) and determine whether treatment should be discontinued. If the subject is discontinued from the study during an Unscheduled Visit, procedures from [REDACTED]

Visit 4 should be followed and the visit will be referred to as an Early Discontinuation Visit.

5. PROCEDURES

5.1 Subject Screening and Enrollment

The study personnel will review the IRB approved informed consent form and assent form, if applicable, with each subject and give the subject an opportunity to have all questions answered before proceeding. The consent/assent form must be signed by each subject and witnessed before the subject is enrolled into the study. A copy of the signed consent/assent will be given to every participant and the original will be maintained with the participant's records. Subjects under the legal age of consent must sign an IRB approved written informed consent/assent in addition to a parent or legally authorized representative.

5.2 Assignment of Subject Number

As possible an independent third-party dispenser will dispense and assign a subject number to each enrolled subject. The subject number will correspond to a computer-generated randomization schedule assigning the number to one of the three study treatment groups.

Once the subject has consented, met inclusion/ exclusion criteria, they will be assigned a subject number. The subject number will be taken from the study medication kit dispensed to the subject at each site.

5.3 Demographics/Medical History

A demographic profile and complete medical history will be recorded prior to starting study medication. The medical history will include a complete review of all current diseases and their respective treatments.

5.4 Concomitant Medications

Concomitant medications and any medications taken [REDACTED] prior to signing informed consent/assent will be recorded as prior/concomitant medications (using their generic name, if known) with the corresponding indication. The medications to be recorded will include prescription and over-the-counter (OTC) medications and dietary supplements. All medications taken on either a regular or "prn" basis, including vitamins, aspirin and acetaminophen, should be recorded on this page prior to commencing the use of the study medication. A record of medication taken by the subject during the study is to be obtained at each study visit including the Week 2/Day 14 (± 4 days) telephone contact.

5.5 Physical Examination

The investigator, sub-investigator or appropriately delegated and qualified designee will perform a brief physical examination, prior to the subject starting study medication. [REDACTED]

5.6 Urine Pregnancy Test

5.7 Dermatological Assessment (Diagnosis)

Investigator or sub-investigator will examine the subject to establish the clinical diagnosis of facial acne vulgaris

5.8 Investigator's Global Assessment (IGA)

To the greatest extent possible, the same investigator who made baseline (Day 1) assessments will perform a Global Assessment of the subject's overall acne vulgaris condition at each subsequent visit.

The following scale will be used for the Investigator's Global Assessment:

Grade	Category	Description
0	Clear	Clear skin with no inflammatory or noninflammatory lesions
1	Almost Clear	Rare non-inflammatory lesions with no more than one small inflammatory lesion
2	Mild Severity	Greater than Grade 1; some noninflammatory lesions with no more than a few inflammatory lesions (papules/pustules only, no nodular lesions)
3	Moderate Severity	Greater than Grade 2; up to many noninflammatory lesions and may have some inflammatory lesions, but no more than one small nodular

		lesion
4*	Severe	Up to many noninflammatory lesions and may have some inflammatory lesions, but no more than a few nodular lesions

*The Case Report Forms will allow for reporting by investigators of lesion worsening beyond Grade 4 with post-visit 1 treatment. Subjects who worsen beyond Grade 4 will be described in the safety evaluation.

5.9 Lesion Counting

Each subject's initial condition and course of acne vulgaris will be assessed by counting the inflammatory, non-inflammatory and nodulocystic lesions (i.e., nodules and cysts) including those present on the nose and documenting on the facial diagram [REDACTED] as part of the source documentation.

[REDACTED]

5.9.1 Inflammatory Lesion Count

The numbers of facial papules and pustules, located above the jaw line to the hairline including those present on the nose, are to be counted at baseline and at each subsequent visit. The type and number of each lesion is to be recorded on the source document at each visit and the total count recorded.

Papule = solid palpable inflammatory lesion \leq 5mm diameter

Pustule = pus-filled inflammatory lesion \leq 5mm in diameter

5.9.2 Non-inflammatory Lesion Count

The numbers of facial open comedones and closed comedones, located above the jaw line to the hairline including those present on the nose, are to be counted at baseline and at each subsequent visit. The type and number of each lesion is to be recorded on the source document at each visit and the total count recorded.

Open Comedones: blackhead, surface of the plugged sebaceous follicle has a blackish appearance

Closed Comedones: whitehead, skin-colored or slightly inflamed "bump" in the skin

5.9.3 Nodulocystic Lesion Count

The numbers of facial nodules and cysts, located above the jaw line to the hairline including those present on the nose, are to be counted at baseline and at each subsequent visit. The total number of this type of lesion is to be recorded on the source document at each visit. Nodules should not be combined into the inflammatory/non-inflammatory lesion counts. Subjects with more than 2 facial nodulocystic lesions should be excluded from the study.

Nodule: Palpable solid or soft lesion $>$ 5mm in diameter.

Cysts: Pus filled lesion > 5mm in diameter

5.10 Application Site Reaction Assessment

At baseline (Visit 1/Day 1) and each subsequent visit, application site reactions such as erythema, dryness, burning/stinging, erosion, edema, scaling/peeling, pain and itching are to be recorded. Pain and itching symptoms will be assessed by discussion with the subject and will be reported [REDACTED]

The Application Site Reaction Assessment must be conducted by qualified investigators listed on the Form FDA 1572 who have been delegated these tasks by the PI. [REDACTED]

[REDACTED]

[REDACTED]

[REDACTED]

Site Reaction	DESCRIPTION
Erythema	[REDACTED]
Dryness	[REDACTED]
Scaling/Peeling	[REDACTED]
Burning/Stinging	[REDACTED]
Erosion	[REDACTED]
Edema	[REDACTED]
Pain	[REDACTED]
Itching	[REDACTED]

SCORE	ASSESSMENT	DESCRIPTION
0	None	[REDACTED]
1	Mild	[REDACTED]
2	Moderate	[REDACTED]
3	Severe	[REDACTED]

5.11 Study Medication Use, Subject Instructions and Diary

At the baseline visit, one [REDACTED] pump bottle of study medication from the subject kit box will be dispensed by the third party dispenser to enrolled subjects along with a diary card. Each subject will also receive a copy of written instructions, which detail the proper application method, and general instructions regarding the study [REDACTED]. The initial application on Day 1 will be demonstrated and observed by study staff when the subject applies the medication at the study site to ensure subjects understand the instructions. Subsequent applications of study medication should be applied as demonstrated starting Day 2. [REDACTED]

[REDACTED] The study staff should instruct the subject to apply all subsequent doses of the study medication once daily (starting on Day 2 of study treatment period) as demonstrated. At all subsequent study visits the study medication will be collected to assess study medication accountability. After the compliance evaluation, empty pump bottles will be collected and kept by the site. Pump bottles with remaining medication are to be redispensed to the subject. In addition to the redispensed pump bottle the subject will receive a new pump bottle each at Visit 2/Week 4/Day 28 (± 4 days) and Visit 3/Week 8/Day 56 (± 4 days). [REDACTED]

[REDACTED]. The study medication kits must be placed in a secure refrigerator 2°C to 8°C (36°F to 46°F) at the investigator site (in an upright position) until dispensed to the subject. Protect from freezing. Once dispensed to the subject, study medication will be stored (in an upright position) at room temperature at or below 25°C (77°F).

[REDACTED] Subjects will cleanse their face with the study provided non-medicated, mild cleanser using only the hands and pat dry with a soft clean towel [REDACTED] before applying the study medication. [REDACTED] the study medication should be applied onto six areas of the face (chin, left cheek, right cheek, nose, left forehead and right forehead) [REDACTED] avoiding contact with the eyes, lips, mouth, broken areas of the skin and mucous membranes at approximately the same time once daily for 12 weeks. Subjects will be instructed to wash hands immediately after applying the study medication. Subjects should continue to use the mild cleanser and facial lotion with sunscreen provided by the sponsor to wash the face for the duration of the study. Subjects will be instructed to not use any other topical treatments or products other than the study provided facial lotion with sunscreen.

A diary card will be dispensed to each enrolled subject at Visits 1, 2 & 3. The subjects will be instructed to complete the diary card after applying each daily dose of study medication. At each subsequent visit, study personnel will review and collect the diary card, determine whether the subject requires counseling for dosage compliance, confirm and record use of any prohibited medications, assess AEs, dispense additional study medication and a new diary as required. In addition, each study subject will be reminded to bring with them all previously dispensed pump

Protocol No: PRG-NY-15-003

bottles (regardless of content) and the completed diary card at the next visit. Study personnel will schedule the subject's next visit prior to the subject's departure.

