5.13 Summary of Assessments

The schedule of visits and procedures to be conducted at each visit are summarized in the Schedule of Study Procedures.

Protocol No: PRG-NY-15-003

^a Schedule next visit if applicable

^f Study medication to be collected and/ or dispensed, if necessary

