6.2.3 Storage and Test Article Accountability

Study medication used to conduct this study will be maintained under adequate security by the investigator or designee. Study medication will be stored in a refrigerator, 2-8°C (36-46°F) in a secured area with limited access. Each investigator site will ensure that the temperature of study medication is monitored and recorded throughout the study. The medication should not be frozen, should be kept in the refrigerator (2-8°C) and kept tightly closed. The investigator will not supply study medication to any person not enrolled in this study, or to any physician or scientist except those named as sub-investigators. Once the pump bottles are dispensed to subjects and exposed to room temperature (RT), they can subsequently be stored at room temperature at or below 25°C (77°F) and the expiration date is 10 weeks only.

Protocol No: PRG-NY-15-003

Each investigator will store at room temperature the Purpose® gentle cleansing wash and Purpose® dual treatment moisture lotion with SPF 15 at the clinic. Upon dispensation the investigator or designee will instruct subjects to store them at home under room temperature.

The clinic personnel will keep a running inventory of study test articles dispensed that will include subject numbers assigned and the date each can of study medication is dispensed, expired and returned. A study medication accountability form will be provided to the investigator to document all medications received, dispensed by and used by each subject. At the conclusion of the study all unused, partially used, and empty containers must be inventoried by the monitor and returned to Perrigo, or designee, for destruction.

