8.1 Statistical Analysis Plan

8.1.1 Analysis Populations

The following populations are defined for the purpose of analyses:

- Intent-to-Treat (ITT) (safety population): Any subject that was randomized received and used study medication.
- Modified Intent-to-Treat (mITT): Any subject, who met the inclusion/exclusion criteria, was randomized, received and used the study medication, and returned for at least one post-baseline efficacy assessment.
- Per Protocol (PP): Any subject:
 - Who met inclusion/exclusion criteria,
 - Who was randomized and received and used study medication,
 - Who met the protocol criteria for compliance [REDACTED]
[REDACTED] and [REDACTED]
[REDACTED]
 - Who completed Visit 4/Week 12/Day 84 (End of Treatment/Early Termination Visit) within window OR was dropped from the study due to treatment failure after at least 4 weeks of treatment with a compliance rate of at least 75%.
 - Without significant protocol violations that could have interfered with the administration of the treatment or the precise evaluation of treatment efficacy.

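### Does returning part-used bottles under Protocol 5.11 conflict with the 10-week room-temperature limit in 6.2.3?

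*Protocol*

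**What the plan says.** Protocol 5.11 has one pump bottle dispensed at baseline and a new one at each of Weeks 4 and 8. Medication is collected at every later visit for accountability. Empty bottles stay at the site. For the others the rule is "Pump bottles with remaining medication are to be redispensed to the subject", and the new bottle comes on top of the returned one. Before each visit, "each study subject will be reminded to bring with them all previously dispensed pump" bottles, whatever their content. Site stock is refrigerated; once dispensed, it is kept at room temperature.

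Protocol 6.2.3 sets the shelf life after dispensing: "they can subsequently be stored at room temperature at or below 25°C (77°F) and the expiration date is 10 weeks only". The same section requires a running inventory that includes "the date each can of study medication is dispensed, expired and returned".

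In Protocol 5.13 the schedule itself is not readable, but one surviving footnote says "Study medication to be collected and/ or dispensed, if necessary".

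The per-protocol (PP) set in Protocol 8.1.1, which is definitive for equivalence under 8.1.4, is limited to subjects "Without significant protocol violations that could have interfered with the administration of the treatment or the precise evaluation of treatment efficacy".

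**The concern.** Treatment lasts 12 weeks, but a bottle lasts 10 weeks once at room temperature. Only the Day 1 bottle can outlive its limit during treatment. In the visible text the return rule is mandatory and looks only at whether gel remains. Neither section refers to the other. A site could hand the Day 1 bottle back at Week 8, and it would then expire at the subject's home with no scheduled contact before Week 12.

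Any use past the limit would fall in the last days before the primary assessment, in a trial whose equivalence conclusion rests on a ratio of mean percent changes. It could also raise a classification question: would a subject who used a bottle that the site had returned under 5.11 count as a significant violator and leave the PP set?

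**Working it through.** **Inputs.** First bottle dispensed on Day 1 (5.11). Limit of 10 weeks = 70 days at room temperature (6.2.3). Visit 2 at Day 28 ± 4, so Day 24-32. Visit 3 at Day 56 ± 4, so Day 52-60. Visit 4 at Day 84 ± 4, so Day 80-88. Study period of 12 weeks, 84 days (Synopsis). Fill size and amount per application are redacted.

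**Limit of the Day 1 bottle.** Counting Day 1 as the first day, the limit is Day 70. Counting 70 days after Day 1, it is 1 + 70 = Day 71.

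**State of that bottle at Visit 3.** Age: 52 - 1 = 51 to 60 - 1 = 59 days, so it is in date on any in-window schedule. Time left: 70 - 60 = 10 days at the least and 71 - 52 = 19 days at the most.

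**Contacts around the limit.** Latest in-window Visit 3 is Day 60, the limit is Day 70-71, and the earliest in-window Visit 4 is Day 80. No scheduled visit falls at the limit.

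**Largest possible overrun, if the subject kept using the Day 1 bottle:**

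| Last use | Days past limit | Share of days treated |
|---|---|---|
| Day 80 | 80 - 71 = 9 to 80 - 70 = 10 | 9/80 to 10/80 = 11.3-12.5% |
| Day 84 | 84 - 71 = 13 to 84 - 70 = 14 | 13/84 to 14/84 = 15.5-16.7% |
| Day 88 | 88 - 71 = 17 to 88 - 70 = 18 | 17/88 to 18/88 = 19.3-20.5% |

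The Day 88 row needs an assumption that the visible text does not make, namely that daily application continues into the visit window. With the stated 84-day period, the bound is 13-14 days.

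**The other bottles.** A Week 4 bottle dispensed as early as Day 24 reaches its limit at Day 93-94. A Week 8 bottle dispensed as early as Day 52 reaches it at Day 121-122. Both fall after Day 88.

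**Can both sections be obeyed?** Section 5.11 governs what the site does with a returned bottle at a visit. Section 6.2.3 governs how long a dispensed bottle may be kept at room temperature, without exception. Returning an in-date bottle at Day 52-60 meets the first, and observing its expiry date meets the second. The subject has been given a further bottle at Week 4 and another at Week 8, both in date to the end of the study. Nothing in 5.11 asks anyone to use gel past 10 weeks.

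**What cannot be seen.** Redactions follow the redispensing and new-bottle sentences in 5.11. The Visit 3 procedures in 5.12.4 and the body of the schedule in 5.13 are not readable. The subject instructions (Appendix B in the contents list) were removed, and 5.11 says that every subject receives written instructions. These are the places where a direction about an expiring bottle would be expected.

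**The case for a change.** The strongest case for a change is that the visible rule in 5.11 is complete and unconditional, and that the protocol itself plans for leftover gel by issuing new bottles in addition to returned ones. The expiry log is only a record: no visible sentence tells staff or subject what to do with a bottle that will expire before the next visit. The remedy would be a few words and no extra visit, and it would settle PP membership in advance.

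Part of this stands. The dates are right, the visible parts of the two sections do not refer to each other, and a cross-reference would be cheap.

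The rest does not carry. An unstated handling step is not a conflict when both rules can be met, and it cannot be called absent when its likely locations are withheld. Overrun needs two further conditions: gel left in the Day 1 bottle at Week 8, and a subject who chooses that bottle over newer ones after about Day 70. Neither can be estimated, and the share affected could be zero. The PP argument is equally open, because deviation text in Protocol 5.15 and part of SAP section 4 are redacted. The documents cannot show that the classification is unsettled.

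**Conclusion.** No change to the plan follows. The two sections fit together on any in-window schedule, and what remains is at most a handling detail that a site tracking expiry dates can settle, if withheld text does not settle it already. The size is bounded: only the Day 1 bottle is concerned, and use past its limit could last at most 13-14 of 84 days for a subject who kept using it. That figure is a calendar bound, not expected exposure. It assumes that gel remains at Week 8, that the bottle has been at room temperature since Day 1, and that dosing ends at Day 84. The documents show no effect on potency, on the Test-to-Reference ratio or on the PP set. A cross-reference between 5.11 and 6.2.3, applying alike to all three arms, would be optional tidying. This conclusion takes no position on how long a bottle should be kept or when it should be withdrawn.
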